Participants will be fitted with a BioNomadix RSP respiratory transducer belt and amplifier. Respiration rate will be recorded with MP160 and digitized using AcqKnowledge at rest and throughout the entire session.

We will test the analgesic effects of light slow brushing, deep pressure, and neutral touch (tapping) on induced pain using a modified affective-CPM paradigm. In this session, we will test the effect of non-painful touch stimuli on the conditioned pain stimulus, as has been conducted by [6, 7]. Both segmental (same dermatome) and nonsegmental (different dermatome) effects will be tested in order to determine whether pain inhibition is a bottom-up neural effect or an indirect affective effect.

After identifying limb locations identified as most comfortable by patients, we will perform calibration and will administer six affective-CPM blocks in an order counterbalanced across subjects: brushing, pressure, and

tapping, repeated with testing within a segment (same dermatome) and outside a segment (different dermatome).

Calibration (psychophysical testing): Session 2 calibration will be confirmed by testing the temperature rated as a 6 in Session 1 and adjusting as necessary.

Each affective-CPM block will include: phasic heat pain (baseline), heat pain with concurrent touch stimulus (test), and then test phasic heat perception once again (post-test), as follows:

Baseline: Heat will be administered using a thermode for 30s. Pain intensity ratings for the heat will be collected every 10s for a total of 3 ratings.

Test: 0-30s: rate pleasantness and intensity of the touch stimulus (brushing, pressure, or tapping). 30-60s: administer heat pain using a thermode concurrently; pain intensity rating of heat pain given every 10sec for a total of 3 ratings

Post-test: Repeat of baseline.

Between blocks the participant will rest for approximately 10-15min until sensation has dissipated to avoid habituation to test stimuli.

Session 2 will occur at the ACTRI and will take approximately 1-2 hours to complete.

Session 3: MRI Session for healthy controls (optional, offered until $N = 20$ controls have completed MRI)

A urine pregnancy (if applicable) test will be performed.

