Cold- and Affective-CPM: We will average the pain ratings from each stimulus period and compare the percent change of baseline to post-test ratings as our primary outcome measure. We will use ANOVA to compare differences between baseline and post-test between touch types, within or between dermatomes/segments, and between patients and healthy volunteers. A linear regression will be used to determine whether baseline touch pleasantness ratings significantly predict the CPM effect for each type of touch.

ASL/fMRI: Periods of baseline pain will be contrasted with periods of touch concurrent to pain (test) and following pain (post-test) in brain areas involved in pain processing. Connectivity analyses will be performed to identify the source of significantly reduced pain response in any of these areas during affective touch.

Inclusion of Women and Minorities:

Participants will include all genders and races. Based on the latest San Diego-based demographic consensus, we plan to recruit 60% White, 16% Asian, 7% Black, .5% Native American, .5% Pacific Islander, 12% Other race, 5% two or more races. We expect that 29% of our participants will be Hispanic or Latino. If necessary to obtain minority representation, under-represented racial groups will be targeted specifically for recruitment.

Rates of FM are higher in females than in males (9:1 ratio) [28], so an approximately 9:1 ratio is expected in the current study. All races and ethnicities will be invited to enroll. Expected demographics are based on the latest San Diego-area demographic census. If needed, to increase minority representation, recruitment efforts will include targeted advertising (e.g., flyers, postings, community outreach presentations) in communities with high minority populations and through community-based talks given by the PI and staff.

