Sensory testing procedures and risks will be described carefully and participants will be encouraged to provide immediate feedback if a stimulus is not tolerable. All participants will be screened to ensure they do not have any history of blood clots of first degree family members with clotting disorders.

All risks to subjects are minimal and unlikely to have significant impact. If subjects are injured by study procedures they will be evaluated by the study physician will be treated by care providers at UC San Diego. Incidental findings such as from MRI will be shared with the subject by a medical provider affiliated with the study and appropriate referrals for follow-up care will be made.

Cold water bath:

Participants will be instructed and reminded that they can remove their hand from the cold water in the event they find it intolerable or do not wish to continue.

Monitoring:

An Independent Monitor (IM) will monitor the activities of this study for purposes of evaluating participant safety and study integrity. The study PI will oversee all experimental procedures of the proposed research activities. In the event of an adverse safety event, protocol deviations and adverse events will be promptly (less than 24 hours) reported to the IMC and the IRB.

This study will follow the Data and Safety Monitoring Plan submitted to NCCIH for the proposed R00 award:

Adverse Event (AE):

An adverse event (AE) is any untoward medical occurrence in a subject during participation in the clinical study or with use of the experimental agent being studied. An adverse finding can include a sign, symptom, abnormal assessment (laboratory test value, vital signs, electrocardiogram finding, etc.), or any combination of these regardless of relationship to participation in the study.

Unanticipated Problems (UP):

The Office for Human Research Protections (OHRP) considers unanticipated problems involving risks to subjects or others to include, in general, any incident, experience, or outcome that meets **all** of the following criteria:

- Unexpected in terms of nature, severity, or frequency given (a) the research procedures that are described in the protocol-related documents, such as the IRB-approved research protocol and informed consent document; and (b) the characteristics of the subject population being studied;

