20. COMPENSATION FOR PARTICIPATION

Participants will receive \$60 for intake/Session 1 and \$60 for Session 2 for a total of \$120. The subset of subjects participating in the MRI session will receive \$120 for the MRI session. A free parking voucher code

will be made available for each study session. If a reschedule is needed, subjects will receive prorated compensation for any partial sessions completed.

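### The six-block CPM analysis is given only as ANOVA with no rule for an incomplete block; a mixed model on all completed blocks should replace it

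*Combined protocol and SAP*

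**What the plan says.** All references are to the combined protocol and SAP.

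- **Design (section 9, Session 2).** The study team "will administer six affective-CPM blocks in an order counterbalanced across subjects": brushing, pressure and tapping, each within and outside the dermatome.
- **Outcome (section 9, Data Analyses and Interpretation).** Ratings are averaged per stimulus period, and the plan will "compare the percent change of baseline to post-test ratings as our primary outcome measure".
- **Method (same place).** "We will use ANOVA to compare differences between baseline and post-test between touch types", and also "within or between dermatomes/segments, and between patients and healthy volunteers". The ANOVA is not called repeated-measures. No analysis set, rule for a missing block or dropout allowance is stated.
- **Signs that a session may be incomplete.** Section 15 says that "participants will be encouraged to provide immediate feedback if a stimulus is not tolerable". Section 14 accepts that pressure may be uncomfortable for some. The Timeline part of section 9 allows one reschedule, for a drug screen failed because of poppy seeds or for technical problems. Section 20 says that, after a reschedule, "subjects will receive prorated compensation for any partial sessions completed".
- **Sample size (section 9).** The group comparison of pain modulation needs 27 per group at an effect size of 0.78. The planned 40 per group comes from a separate regression needing 77.

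**The concern.** Two of the three ANOVA factors are within-person, so each participant contributes six linked values. A classical repeated-measures ANOVA needs all six. Someone who misses one pressure block then also loses valid brushing and tapping blocks.

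If the missing blocks are unrelated to response, the cost is precision. If people stop because touch or heat goes badly for them, and this happens more in one group, the complete cases no longer represent that group. In FM this would matter most, because altered response to touch is what the study sets out to measure. Replacing non-completers to reach 40 per group would restore the count but not remove the selection.

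**Working it through.** **1. The plan's own figures.** Two-sample t-test, noncentral t, d = 0.78, two-sided 0.05 (two-sidedness and 80% power assumed for this comparison): power is 80.3% at 27 per group and 78.8% at 26, so the stated 27 reproduces. Overall F test of three predictors with f² = 0.15: N = 77 reproduces. That regression predicts brushing pleasantness and does not use the six blocks.

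**2. Time pressure in Session 2.** The plan says "Between blocks the participant will rest for approximately 10-15min". Five rests take 5 × 10 to 5 × 15 = 50 to 75 minutes. Each block has 30 s baseline, 60 s test and 30 s post-test, so six take 6 × 2 = 12 minutes. That is 62 to 87 minutes before urine tests, belt fitting and calibration, in a visit put at 1 to 2 hours. An unfinished session is therefore foreseeable.

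**3. Participants dropped by a complete-case ANOVA.** The documents give no missing rate, so q (the share of blocks missing, independently) is assumed. Share dropped = 1 − (1 − q)^6; complete cases per group = 40 × (1 − q)^6; blocks kept by an all-available-data model = 240 × (1 − q).

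| q | Dropped | Complete of 40 | Blocks kept of 240 |
|---|---|---|---|
| 1% | 5.9% | 37.7 | 237.6 |
| 2% | 11.4% | 35.4 | 235.2 |
| 3% | 16.7% | 33.3 | 232.8 |
| 5% | 26.5% | 29.4 | 228.0 |

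Independence gives high figures. If the same 5% of blocks were lost only as pairs of pressure blocks, 0.05 × 6 / 2 = 15% of participants would be dropped. If whole sessions were lost, 5% would be dropped, and a mixed model would recover none of them.

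**4. Power for the group comparison (d = 0.78).** It is 93% at 40 vs 40. At 5% missing in FM and 1% in controls (29 vs 38) it is 88%. FM falls to 27 only at q = 1 − (27/40)^(1/6) = 6.3%. Power for the interactions cannot be computed, because the plan gives no inputs for them.

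**5. Bias.** Simulation with 40 per group, six blocks, within-person correlation 0.5, no true group difference and loss in FM only (all assumed), at rates leaving about 29 to 30 complete FM cases. Units are the SD of a single block value; a negative value makes FM look more responsive to touch than it is.

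| Loss depends on | Complete cases | All available blocks |
|---|---|---|
| nothing (random) | 0.00 (SE 0.19) | 0.00 (SE 0.17) |
| earlier observed responses | −0.19 | 0.00 |
| the unobserved response | −0.18 | −0.04 |

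**6. Which mixed model.** With complete data, participant-by-touch has 78 × 2 = 156 error df, and the other within-person strata have 78 + 156 = 234. Let v be the participant-by-touch variance relative to a residual of 1. The touch-by-group mean square then has null expectation 1 + 2v. A random-intercept-only model divides it by the pooled error, (156(1 + 2v) + 234)/390 = 1 + 0.8v. The ratio is 1.25, 1.43 and 1.67 at v = 0.25, 0.5 and 1, and a nominal 5% test then rejects about 9%, 12% and 16% of the time. The repeated-measures ANOVA stays at 5%.

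**The case against.** The plan says only ANOVA, so listwise deletion is an inference. That is correct, but the inference is the natural one for within-person factors. The other reading, an ordinary ANOVA on up to 80 × 6 = 480 values treated as independent, ignores clustering and would be worse. Either way the text needs changing.

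Three stronger readings are tempting and are not supported:

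- **That FM data will be lost selectively.** No passage says so, and several features work against it. Heat is set for each person to 6 out of 10 and rechecked in Session 2. People who cannot be calibrated at 50C or lower are excluded. Limb sites are chosen for comfort, sleeve pressure stays below 100 mmHg, and the touch types are introduced in Session 1. On the other side, only heat is calibrated, and the study expects FM participants to find touch less pleasant. Selective loss remains possible.
- **That the plan provides for stopping within the six blocks.** The explicit permission, that "they can remove their hand from the cold water in the event they find it intolerable", concerns the Session 1 cold bath. For the six blocks there is only the invitation to give feedback, and the partial-session payment is tied to rescheduling.
- **That the power statement fails.** The 40 per group belongs to the pleasantness regression. This comparison needs 27, and 29 vs 38 still meets that.

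It is also fair that a mixed model is no complete cure. It cannot help people with no Session 2 data, and some bias remains if stopping depends on responses never observed.

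**Conclusion.** The point holds as a gap with a better method available. A six-block within-person outcome is analysed by an unspecified ANOVA with no rule for incomplete blocks, and incomplete sessions are foreseeable. At assumed rates of 1% to 5% of blocks missing independently, the natural form would drop about 6% to 26% of participants, and fewer if losses cluster within person. The reason to act is possible bias and lost precision, not power for the group comparison. The simulated bias of about 0.19 SD rests wholly on assumed FM-only, response-related stopping; it shows what could happen and is not a forecast. Whether FM participants would stop more often cannot be settled from the documents.

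**What to change.** Replace the ANOVA sentence by a linear mixed model fitted by REML to all completed blocks, with Kenward-Roger or Satterthwaite degrees of freedom:

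- **Fixed effects:** group, touch type, segment, their interactions, and block order.
- **Random effects:** participant, participant-by-touch-type and participant-by-segment, or alternatively an unstructured within-person covariance. A participant intercept alone is not enough (step 6 of the working). With these terms the tests match the repeated-measures error terms when data are complete.
- **Analysis set:** everyone with at least one completed block.
- **Reporting:** number of missing blocks and reasons, by group.
- **Sensitivity analysis:** the complete-case repeated-measures ANOVA.

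The cost is a few sentences of analysis text, standard software and slightly more analysis work. The covariance structure may need simplifying if the model does not converge, so the order of simplification should be stated in advance.

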
The proposed research is the subject of a pending R00 award and will determine whether light and deep pressure touch have comparable analgesic effects, and whether these effects differ in individuals with chronic pain conditions. It will also determine which factors predict the blunted affective touch perception observed in patients with chronic pain. The central hypothesis is that both light and deep pressure touch exert analgesic benefits, and that these analgesic effects will correlate with the pleasantness of touch. Further, we predict that the analgesic effects of pleasant touch will be reduced in patients with chronic pain, who experience reduced touch pleasantness. This research will advance our understanding of the mechanisms of massage therapy and its effect on those who suffer from chronic pain.

Aim 1 (R00): Determine why individuals with chronic pain show reduced C-LTMR-related touch pleasantness.

Hypotheses: I hypothesize that blunted pleasantness of C-LTMR and deep pressure touch in individuals with chronic pain will be predicted by psychological factors including depression and trauma history (due to the impact of these factors on the μ -opioid system, e.g. [9]).

Aim 2 (R00): Determine whether the analgesic effects of light and deep pressure touch are reduced in individuals with chronic pain, and whether analgesia correlates with pleasantness perception.

Hypotheses: I hypothesize that concurrent or recent administration of light or deep pressure pleasant touch will reduce the perceived pain of a phasic heat stimulus, and that this effect will be reduced in chronic pain patients. Further, I predict that the analgesic effect of affective touch will be correlated with the perceived pleasantness of the touch.

Sub-aim 2b: Determine whether CPM effects of pleasant touch are related to CPM effects of pain.

Hypotheses: I hypothesize that the CPM efficiency for painful and pleasant touch will not be correlated across participants, suggesting divergent mechanisms.

Sub-aim 2c: Determine whether analgesic effects of light stroking or deep pressure are mediated by reductions in respiration rate.

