The proposed research will compare the analgesic effects of light and deep pressure touch to those of neutral touch, determine whether the effects are direct (segmental), and determine whether these effects differ in individuals with chronic pain conditions. It will also determine which factors predict the blunted affective touch perception observed in patients with chronic pain. Finally, it will include continuous respiration monitoring during affective and pain testing to determine whether slower respiration rate underlies (mediates) the analgesic effects of pleasant touch. The central hypothesis is that both light and deep pressure pleasantness are blunted in individuals with chronic pain primarily due to psychological factors, and that the analgesic effects of pleasant touch will also be reduced in patients with chronic pain. Further, we predict that pleasant touch will exert greater (nonsegmental) analgesic benefits than neutral touch, and that this analgesic effect will correlate with the pleasantness of touch. This research will advance our understanding of the mechanisms of massage therapy and its effect on those who suffer from chronic pain.

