We expect that FM patients will show reduced pleasantness of C-LTMR-optimal touch compared to healthy individuals as found in FM patients in [3] and LBP patients in [8]. We hypothesize that current depression and trauma history will be significant predictors of blunted C-LTMR touch pleasantness. Based on an effect size F^2 of 0.15, three predictors, alpha of 0.05, and power 0.8, this study will require $N = 77$ participants. We will round up to $N = 80$ and include $N = 40$ FM patients and $N = 40$ healthy controls. Based on effect sizes observed in [3] and [8], this sample size will also be sufficient for the comparisons of pleasant touch.

Furthermore, we expect that FM patients will show reduced analgesic benefit of pleasant touch compared to healthy controls, due to reduced touch pleasantness ratings and our theorized relationship between touch pleasantness perception and analgesia, and due to reduced endogenous pain modulation evidenced in the CPM paradigm. We expect reduced analgesic effects of touch pleasantness in FM due to altered pleasant touch perception in FM (and LBP) [3, 8]. The studies showing analgesic effects of affective touch showed effect sizes of approximately $d = 0.6$ [6] and $d > 2$ (for the large compression area) [7], respectively. We would need 24 participants to demonstrate the smaller effect size in each group (alpha of 0.05, power of 0.8). No previous study has examined how pleasant touch modulates pain in chronic pain compared to healthy adults. To observe a difference in affective pain modulation between patients and healthy controls, based on the average large effect size of 0.78 seen across studies in [27] for CPM, this study would require 27 participants in each group, so the 40 participants calculated for each group will be sufficient. The MRI portion of the study will be a pilot study ($N = 20$), intended to provide preliminary data for future grant applications.

Data Analyses and Interpretation

Scores on the depression and trauma history questionnaires will be used as linear regressors to predict ratings of gentle brushing pleasantness.

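### The Aim 2 regression of analgesia on touch pleasantness names no group term and no analysis set; if both groups are pooled, group alone can produce the association for brushing and pressure

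*Combined protocol and SAP*

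**What the plan says.** **Aim 2.** The hypothesis in Section 6 is that "the analgesic effect of affective touch will be correlated with the perceived pleasantness of the touch"; it is not restricted to patients or to controls. The matching analysis in Section 9 is a single sentence: "A linear regression will be used to determine whether baseline touch pleasantness ratings significantly predict the CPM effect for each type of touch". It names no group term, interaction, within-group fit or analysis set. The sentence before it, on the ANOVA, does name group: "within or between dermatomes/segments, and between patients and healthy volunteers".

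**Expected group differences.**
- Predictor: Section 9 (Sample Size Determination & Power) states "We expect that FM patients will show reduced pleasantness of C-LTMR-optimal touch compared to healthy individuals", and Section 7 extends this to pressure: "both light and deep pressure pleasantness are blunted in individuals with chronic pain primarily due to psychological factors". No FM difference in pleasantness is stated for tapping.
- Outcome: "we expect that FM patients will show reduced analgesic benefit of pleasant touch compared to healthy controls". Two reasons are given. One is lower pleasantness. The other is "due to reduced endogenous pain modulation evidenced in the CPM paradigm".
- Size: the patient-control comparison of touch analgesia is sized "based on the average large effect size of 0.78 seen across studies in [27] for CPM".

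**Aim 1.** The sample size (N = 77, rounded to 80) uses f² = 0.15 and three predictors. The analysis names two regressors, depression and trauma history, and no analysis set. Section 6 words the hypothesis for people with chronic pain, while N = 77 can be reached only by counting both groups.

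**The concern.** Aim 2 asks whether people who find a touch more pleasant get more pain relief from it. On the plan's own expectations, FM status lowers both variables, and one of its routes to lower analgesia bypasses pleasantness. Group is then a common cause of predictor and outcome. A pooled slope without group mixes the association among comparable people with the difference between the two group means. A positive result could mean only that patients and controls differ on both measures, and nearly all such errors would fall in the hypothesised direction.

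For Aim 1, the unnamed third predictor and the missing analysis set leave open which model was powered and whether the usable n is 80 or 40.

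**Working it through.** **1. The plan's own figure.** For a joint F test in linear regression, λ = f²·N, with u tested predictors and v = N − p − 1 for p predictors in the model. With f² = 0.15, u = p = 3 and α = 0.05:
- N = 76 gives power 0.796.
- N = 77 gives λ = 11.55, v = 73 and power 0.802.

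So N = 77 is correct for three predictors tested jointly. Two predictors need N = 68 (power 0.804).

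**2. Aim 2: association produced by group alone.** Inputs are 40 + 40 (Section 9), an analgesia gap dy = 0.78 (Section 9, borrowed from CPM studies) with dy = 0.4 as an assumed lower value, and pleasantness gaps dx = 0.3 / 0.5 / 0.8, all assumed because the plan gives none. With equal groups, unit within-group SD and zero within-group association, the pooled correlation is

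r = 0.25·dx·dy / √[(1 + 0.25·dx²)(1 + 0.25·dy²)].

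For dx = 0.5 and dy = 0.78: 0.0975 / √(1.0625 × 1.1521) = 0.0975 / 1.106 = 0.088.

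The false-positive rate is the chance that a two-sided 5% test rejects. The Fisher z approximation uses m = atanh(r)·√77 and P = Φ(m − 1.96) + Φ(−m − 1.96). For r = 0.088, m = 0.775 and P = 0.118 + 0.003 = 0.121. Simulation (20,000 trials per scenario) agrees to within half a percentage point:

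| dy | dx | r | Fisher z | Simulated, no group | Simulated, with group |
|---|---|---|---|---|---|
| 0.78 | 0.3 | 0.054 | 7.6% | 7.6% | 5.1% |
| 0.78 | 0.5 | 0.088 | 12.1% | 11.8% | 5.0% |
| 0.78 | 0.8 | 0.135 | 22.2% | 22.3% | 4.9% |
| 0.4 | 0.3 | 0.029 | 5.8% | 5.4% | about 5% |
| 0.4 | 0.5 | 0.048 | 7.0% | 7.3% | about 5% |
| 0.4 | 0.8 | 0.073 | 9.8% | 9.7% | about 5% |

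These are rates per touch type, and apply to brushing and pressure only.

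**3. Price of the group term.** The standard error of the pleasantness slope grows by √(1 + dx²/4) before any gain from lower residual variance: √1.0225 = 1.01, √1.0625 = 1.03 and √1.16 = 1.08, or about 1% / 3% / 8%.

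**4. Aim 1.** At f² = 0.15 for the two named predictors:
- All 80, given group (u = 2, v = 76, λ = 12): power 0.87, if 0.15 is read as the partial f².
- FM only (n = 40, u = 2, v = 37, λ = 6): power 0.55.

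If the groups are pooled without group, the joint two-predictor test can also be inflated. Assumed gaps (pleasantness, depression, trauma, in SD) of (0.3, 0.5, 0.3), (0.5, 1.0, 0.5), (0.8, 1.0, 0.5) and (0.8, 1.5, 0.7), with an assumed within-group depression-trauma correlation of 0.3 and no within-group link to pleasantness, give about 6%, 13%, 24–26% and 43%. With group in the model the rate is about 5%.

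**The case against.** **Pooling is not stated.** A reader might infer that the plan commits to fitting all 80 without group. It does not; the analysis set is simply absent. A separate regression in each group fits the text equally well and removes the bias. This stands, so the Aim 2 point is conditional on pooling.

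**The 0.78 is generous.** It comes from conventional CPM studies, and Sub-aim 2b hypothesises that modulation by pain and by pleasant touch are uncorrelated, so the deficit need not carry over to touch. The plan also names lower pleasantness as a reason for lower analgesia. Any part of the gap that arises that way is real signal. This also stands: 22% is not the expected error rate, and with smaller gaps the inflation almost vanishes. Against it, the plan itself uses 0.78 to size the touch comparison.

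**Pleasantness may carry the group effect, so adjusting could remove the signal.** This does not stand for the slope. Group precedes pleasantness, and conditioning on it leaves the within-group association intact at a small cost in precision.

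**Aim 1 is weaker.** A reader might infer that Aim 1 is biased in the same way, or underpowered. The documents support neither. No passage states that FM patients differ from controls on depression or trauma; attributing blunted pleasantness to psychological factors suggests it, but as a hypothesis. The Section 6 list of factors is open-ended, so a third predictor is no contradiction. N = 80 exceeds the 68 needed for two predictors if the groups are pooled.

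**Conclusion.** The Aim 2 point holds as a conditional specification fault. As written, the model permits a pooled fit in which group can create the hypothesised association for brushing and pressure. Over assumed pleasantness gaps of 0.3 to 0.8 SD, the false-positive rate per touch type runs from about 7–8% to 22% if all of d = 0.78 bypasses pleasantness, and from about 5% to 10% at d = 0.4. It is about 5% once group is included. These figures assume 40 + 40 completers, equal within-group variances and no within-group link. The argument does not extend to tapping, and the primary ANOVA of percent change is untouched.

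The Aim 1 point is a request for clarification: a third predictor that is counted but not named, and an analysis set that could be 80 or 40. The stated N is arithmetically right, and power is in question only if patients alone are analysed (about 55% at f² = 0.15).

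**What to change.** **Aim 2.** State that each pleasantness regression is fitted on all 80 participants with group as a covariate, and that pleasantness is judged by its coefficient given group. Show the slopes within FM and within controls descriptively. The cost is one degree of freedom per model and a standard error about 1–8% larger over the range assumed here; no new data are needed.

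**Aim 1.** Name the third predictor and the analysis set. If all 80 are used, make group the third predictor, so that depression and trauma are tested as within-group associations. That alone does not explain why pleasantness is lower in FM, so also report the group coefficient with and without depression and trauma. If FM only is meant, say so and restate the power for n = 40. Tie the sample-size sentence to the test that will be used. The cost is wording, plus one degree of freedom if group is added.
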